### **Adverse Event Reporting**

Baseline conditions at study entry will be noted and documented during screening/baseline medical history. Changes in health status and disease progression will be collected as part of interval history and will not be evaluated as adverse events. Clinical data such as medication use, seizure history, and EEG activity will be collected as part of interval medical history and recorded for the determination of disease development.

Adverse events will be defined as those relating to study procedures including neurodevelopment and EEG will be tracked on an Adverse Event log. Adverse Events will be categorized using the Common Terminology Criteria for Adverse Events (CTCAE) CTCAE version 4.0.

Each procedure related adverse event (AE) will also be graded for severity as follows:

**Mild**-Discomfort noticed, but no disruption of normal daily activity.

**Moderate**-Discomfort sufficient to reduce or affect normal daily activity.

**Severe**-Incapacitating, with inability to work or to perform normal activity.

Adverse Events (AEs) will also be determined to be *expected* or *unexpected* events. An *unexpected adverse event* is any adverse event occurring in subjects participating in the study, for which the nature, severity, or frequency of the event is not consistent with the foreseeable risks associated with the procedures involved in the research, as described in the study-related documents or literature regarding the procedures, or the expected natural progression of any underlying disease, disorder, or condition of the subject experiencing the adverse event.

Adverse events that require capture are to be reported per local IRB requirements and reported on a regular basis as outlined in the Manual of Procedures.

For this study, a *Serious Adverse Event* (SAE) is defined as any untoward medical occurrence that results in death; is life threatening; requires inpatient hospitalization or prolongation of an existing hospitalization; results in persistent or significant disability/incapacity; is any other untoward significant medical event, which may not be immediately life threatening or result in death or hospitalization but may jeopardize the patient or may require interventions to prevent one of the outcomes listed above. Also included are untoward behavioral, psychosocial or legal events which may jeopardize the subject, as determined by the investigator. SAEs at least possibly related to study participation, should be reported within 1-2 business days of the site's knowledge of the event. Each site should report related SAEs to their institution as per local and institutional requirements.

The SAEs will also be reviewed by the medical safety monitor (Dr. [name]) for relatedness to the study. All SAEs that are at least "possibly, probably, or definitely" related to the study will be reported to the site IRB (if applicable) and lead PIs as soon as possible. The lead PI, Dr. [name], will be asked to review these *related* SAE reports within 72 hours of receipt of report.

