### **Secondary Study Objectives:**

- 1) Determine the effectiveness of early versus delayed treatment with vigabatrin in clinical seizure prevention. The outcome measure will be time to first clinical seizure following randomization. The prevalence of drug-resistant epilepsy will be assessed at 24 months for each group (vigabatrin early treatment vs. vigabatrin delayed treatment).
- 2) Determine the impact of early versus late treatment on the other components of the Bayley-III (receptive communication, expressive communication, fine and gross motor skills) and risk of autism spectrum disorders (ASD). The primary outcome measures for this objective will be subdomain scores of the Bayley-III, Vineland-II (Survey Interview Form), Beery Visual Motor Integration (VMI), and ADOS2 at 24 months. Additional exploratory analysis will be completed at 36 months to assess changes observed at 24 months are consistent with those seen at 36 months and indicative of long-term outcome. At 36 months of age subjects will also complete the Peabody Picture Vocabulary Test (PPVT). During the COVID-19 Pandemic in order to minimize the risk of infection to observer and infant until the completion of the study the Brief Observation of Symptoms of Autism (BOSA) will be administered at 24- and 36-month visits. Additionally, the ADI-R will be administered at the 36-month visit.
- 3) Confirm vigabatrin safety as a preventative treatment for clinical seizures in infants with TSC. The outcome measure will be percentage of patients in each group (vigabatrin early treatment vs. vigabatrin delayed treatment) with treatment associated adverse events (AEs), serious adverse events (SAEs), and risk evaluation and mitigation strategy (REMS) measures.
- 4) Confirm of the feasibility of using EEG biomarkers to identify TSC infants at risk for developing epilepsy. The outcome measure will be the sensitivity and specificity of EEG epileptiform activity in predicting epilepsy outcomes at 24 months within treatment groups.

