Additional developmental measures and ASD Risk: The sub-scores on the Bayley-III and the composite score estimated using Hotelling’s  $T^2$ . The power for this endpoint will vary, but is expected to be similar to the primary. In the children with Pervasive Developmental Disorders, the effect sizes versus normal matched controls were 1.77, 1.67, 1.17 and 1.33 for the Receptive communication, Expressive Communication, Fine and gross motor sub-scores respectively. The ADOS2 will be completed at 24 and 36 months of age as a neurodevelopmental assessment for symptoms of ASD. The results from Study Arm A (seizure free, no treatment), Arm B (VGB versus. Placebo), and subjects with electrographic seizures at baseline EEG who move directly into Open Label treatment will be compared increasing our power to assess differences (Figure1).

Determination of vigabatrin safety as a preventative treatment for clinical seizures in infants with TSC will be assessed using comparison between the treatment groups and as a summary of exposure time on the drug. The outcome measure will be percentage of patients in each group (vigabatrin early treatment vs. vigabatrin delayed treatment) with treatment associated adverse events (AEs), serious adverse events (SAEs), and risk evaluation and mitigation strategy (REMS) measures. Treatment related AEs and SAEs will be monitored and tabulated. Given the expectation that the delayed group will cross-over to active treatment sooner than the early treatment group, adverse events will be characterized using life table approaches to ensure adjustment for exposure time. Thus, counts of individuals with AEs, total number of specific AEs and rate per months of follow-up will all be provided and assessed for any differences and for the safety population (early plus late on person years of exposure basis). Events of specific interest and risk evaluation and mitigation strategy (REMS) measures will be compared, including any and all ophthalmologic problems that may arise. Data from the negative control group (estimated to be approximately 15-20 patients) will also be used to compare the occurrence of AEs and SAEs.

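### The adverse event definition is tied to study procedures and never mentions study drug, although the safety objective needs treatment-associated events by group

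*Combined protocol and SAP*

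**What the plan says.** Secondary Study Objectives, item 3, sets the safety outcome: "The outcome measure will be percentage of patients in each group (vigabatrin early treatment vs. vigabatrin delayed treatment) with treatment associated adverse events (AEs", together with SAEs and REMS measures. The safety paragraph of the Analyses section repeats this and adds: "Treatment related AEs and SAEs will be monitored and tabulated". Because the delayed group is expected to cross over to active drug sooner, it plans life-table methods to adjust for exposure, and promises that "counts of individuals with AEs, total number of specific AEs and rate per months of follow-up will all be provided". It also compares AEs and SAEs with the negative control group.

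Adverse Event Reporting states what an AE is:

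- Definition: "Adverse events will be defined as those relating to study procedures including neurodevelopment and EEG will be tracked on an Adverse Event log".
- Severity: "Each procedure related adverse event (AE) will also be graded for severity as follows".
- Expectedness: an event is unexpected if it is not "consistent with the foreseeable risks associated with the procedures involved in the research" or with the natural course of disease.
- Exclusion: "Changes in health status and disease progression will be collected as part of interval history and will not be evaluated as adverse events".
- Reporting: "Adverse events that require capture are to be reported per local IRB requirements", with the schedule left to the Manual of Procedures.

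The definitions in that section do not mention vigabatrin, placebo or study drug.

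**The concern.** The analysis asks for one kind of event and the collection rule defines another. Treatment-associated AEs by group can be tabulated only if events possibly due to the drug are recorded as AEs in the first place. A site that follows Adverse Event Reporting to the letter would put a non-serious drug reaction into interval history, where it is not evaluated as an AE.

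The stake is the non-serious AE part of objective 3. Under the literal rule that table would hold mainly procedure events. These would be expected in both randomised arms, since the arms share one visit schedule. The comparison would then be pulled toward no difference, and a reassuring table could be a product of the definition. This matters because the Background itself cites potential side effects in otherwise asymptomatic infants as a reason why presymptomatic treatment was hard to justify. If sites read the section differently, the AE rate would also depend on site practice.

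**Working it through.** No arithmetic decides this point. The check sets the sections side by side, looks for another route by which the events could be captured, and follows one event through the rules.

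**Step 1: definition against use.**

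| Element | Adverse Event Reporting | Objective 3 and Analyses |
|---|---|---|
| What counts as an AE | Events relating to study procedures; the examples are neurodevelopment and EEG | Events associated with treatment, by group; AEs in general for the negative controls |
| Severity | Grading specified for procedure-related AEs | Treatment-related AEs are tabulated, but this scale is not specified for them |
| Expectedness | Procedure risks or disease course | Drug risks are not a reference, although the Background says the side effect profile is known |
| Relatedness to drug | Not mentioned for AEs | Needed to call an AE treatment associated |
| Changes in health | Interval history, not evaluated as AEs | Counts and rates per months of follow-up |

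**Step 2: other capture routes.**

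- SAEs: Adverse Event Reporting defines these by seriousness and does not limit them to procedures. The Data and Monitoring Plan has the safety monitor code association with trial drug. Not affected.
- Eye findings and REMS measures: collected on a schedule under Ophthalmologic Assessments. Not affected.
- MRI: Protocol description counts vigabatrin-related changes on routine clinical MRI as safety data. Not affected.
- Tracking system: the Data and Monitoring Plan generates a record for every AE and SAE, but does not define an AE and describes drug-association coding for SAEs only.
- DSMB: Study Organization and Data Management provides quarterly reports from the coordinating center. They can show only what was recorded.

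No route in the document expressly covers a drug reaction that is non-serious and is neither an eye nor an MRI finding.

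**Step 3: one event.** Take a child in the blinded phase with a non-serious complaint, unrelated to an EEG or a developmental test, that the investigator thinks may be due to study drug. Under Adverse Event Reporting, read literally, it is not procedure related, so it is not an AE. It is a change in health status and goes to interval history. Under Analyses it must appear in the treatment-related AE table. Both cannot be followed.

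**Step 4: who is covered.** From the sample-size text under Primary Study Objective: 47 randomised + 28 not randomised = 75, and 50 + 30 = 80. The definition applies to all of them. The documents' estimates of untreated children are 15 to 20 (Analyses, negative control group) and 24 (Vigabatrin and Placebo, Arm C: 0.30 × 80 = 24).

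**Step 5: size.** A bias calculation would need AE rates by arm, the rate of procedure events, and the fraction of drug reactions recorded. The documents give none of these.

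**The case against.** The strongest reply is that the section can be read more widely.

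- The exclusion of health-status changes stands between a sentence on baseline conditions and one on seizure history and EEG activity. In that setting it may mean only the course of TSC and epilepsy, which is a legitimate exclusion.
- A separate sentence categorises AEs by CTCAE version 4.0 without limiting them to procedures. Procedure-related AEs could then be a subset given an additional grade.
- The definition sentence is ungrammatical, so its limiting force is open to argument.
- Analyses directly commits to monitoring treatment-related AEs.
- The Manual of Procedures, not supplied, may hold a wider rule.

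Much of this stands. It shows that loss of drug reactions is not established. It does not remove the conflict: the one definition given still rests on procedures, the expectedness rule names procedures and disease course only, and drug relatedness is described for SAEs alone. A wider Manual would still disagree with the protocol. The room for different readings is itself how capture could come to vary by site.

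It can also be said that adding study drug to the definition would be enough. That would cover objective 3. It would not serve the negative control comparison, since children who never receive study drug cannot have a drug-related event.

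**Conclusion.** The point holds as a conflict within the document. The wording of Adverse Event Reporting cannot supply the AE data that objective 3 and Analyses call for, and it should be corrected. Confidence is high for the textual conflict. It is lower for the consequence, which rests on the assumption that sites follow the section literally.

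The reach is limited to non-serious events other than eye and MRI findings, in one component of one secondary objective. All 75 to 80 expected children fall under the definition.

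A reader might infer more than the documents support:

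- That the safety objective as a whole fails, or that drug reactions will be lost. The unaffected components and the possible wider reading rule this out as a firm conclusion.
- That the bias can be sized. Any figure would rest wholly on assumed rates.
- That 28 to 30 children form a never-treated comparator. That figure counts children not randomised. Protocol description sends some unrandomised children to open-label vigabatrin, and Additional measures and analyses considerations includes vigabatrin-treated children in the 28 to 30.
- That the negative control comparison is itself misstated. Its wording refers to AEs and SAEs without a treatment-associated limit; the difficulty lies in the definition that feeds it.

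**What to change.** Reword Adverse Event Reporting as follows:

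1. Define an AE as any untoward medical occurrence, whether or not procedure related, in line with the SAE wording already in that section. Collect AEs in the same way in all groups, including untreated children.
2. Grade severity for all AEs.
3. Record relatedness to study drug as well as to study procedures.
4. Judge expectedness against study-drug risks as well as procedure risks.
5. Limit the health-status exclusion to the course of TSC and epilepsy (seizures, EEG change), which is analysed as outcome data.
6. Align the Manual of Procedures with the new text.

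The cost is a wording change, an edit to the AE form and more AE entry at sites. Because the protocol is already at Version 6.0, AE capture may differ before and after the change. The date should be recorded and the difference disclosed with the AE tables. Earlier interval history can be recoded only where it holds enough detail, such as onset and severity; the rest should be reported as a limitation.

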- *Supports transfers of participants from one site to another*: Based on our experience in trials, we have been able to plan our system to seamlessly allow for movement of participants from one location to another either due to participant relocation or a site closure (both have occurred in our trials). Our estimated rates of participant moves are about 5 percent, and when not planned for in advance, often cause ad hoc solutions and confusion; however, in the PREVeNT Trial the procedures will already be in place.
- *Assists in ensuring participant safety*: With each AE/SAE in the trial, a tracking system of the event is generated. When SAE CRFs are entered, the safety monitor is notified of the event through an automatically generated email as are pre-specified key individuals (the Chair or members of the DSMB, NINDS representative, appropriate DCC, etc.). Reminders are sent until the email is opened and the alert acknowledged online in the DCC web-based system. The safety monitor has access to the details of the SAE through a separate interface to the system, and as he/she codes the SAE (determining likelihood of association with trial drug, severity of the SAE, the expected/unexpected nature of the event, and the resolution of the event), the event can be closed and locked in the system. If appropriate, tracking of the event over time is also monitored to determine its resolution or continued severity, and also the duration of the process.

Each site will use trained personnel from their institution who are independent of this trial to conduct monitoring visits twice a year. The UAB Center for Clinical and Translational Science (CCTS) group will serve as UAB site monitor. This includes both regulatory and clinical. Each site will be monitored at the site level and summary monitoring report will be emailed to UAB addressing any action items. All monitoring reports will be sent to UAB IRB.

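### The protocol sets a reporting deadline only for SAEs thought at least possibly related, and an event attributed to TSC may produce no SAE form at all

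*Combined protocol and SAP*

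**What the plan says.** Adverse Event Reporting defines an SAE by outcome and seriousness, with no condition on cause. It then sets the reporting time: "SAEs at least possibly related to study participation, should be reported within 1-2 business days" of the site learning of the event. It adds that "The SAEs will also be reviewed by the medical safety monitor", who assesses relatedness; this sentence has neither a relatedness limit nor a time limit. SAEs that are at least possibly related "will be reported to the site IRB (if applicable) and lead PIs as soon as possible", and the lead PI is asked to review these related "SAE reports within 72 hours of receipt of report".

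The same section, in its opening paragraph, records changes in health and progression of disease as interval history and excludes them from adverse event assessment. It leaves regular adverse event reporting to local IRB requirements and the Manual of Procedures.

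The Data and Monitoring Plan is broader. "With each AE/SAE in the trial, a tracking system of the event is generated", and "When SAE CRFs are entered, the safety monitor is notified of the event through an automatically generated email as are pre-specified key individuals"; the examples given include the DSMB chair or members and an NINDS representative. Reminders continue until the alert is acknowledged. The safety monitor then codes relatedness, severity and expectedness.

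Under Analyses, the safety paragraph says "Treatment related AEs and SAEs will be monitored and tabulated". It also promises counts of children with AEs, event counts and rates by follow-up time, and a comparison of AEs and SAEs with the untreated negative controls.

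**The concern.** The safety monitor is meant to judge relatedness, yet a relatedness judgement has to come first to start the only reporting clock. If the site makes that judgement, a preliminary opinion decides which events reach central review promptly. The population makes this matter. The infants are seizure-free at entry but have a serious multisystem disease, so a hospital admission is easily put down to TSC. A drug-related event first taken for disease is the kind of event that central review exists to catch.

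The disease-progression rule adds a second filter. An event handled as interval history might generate no SAE form, and without a form the alert has nothing to act on.

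**Working it through.** The plan gives no figure to reproduce. The check sets the provisions side by side, according to the first view taken of the event.

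| Step | Thought at least possibly related | Thought unrelated |
|---|---|---|
| Report after the site learns of it | 1-2 business days | No limit stated |
| Entry of the SAE form | No separate limit stated | No limit stated |
| Alert to monitor and key individuals | Automatic on entry | Automatic on entry |
| Monitor's relatedness review | No limit stated | No limit stated |
| Site IRB and lead PIs | As soon as possible | Only if found related on review |
| Lead PI review | 72 hours from receipt | Only if found related on review |

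**1. Where the columns differ.** The 1-2 day rule is the only time limit on getting an event out of the site, and it is missing from the right-hand column. The alert is the same in both columns, but it starts at form entry. The Data and Monitoring Plan expects data to be recorded first on paper and entered after the participant encounter. It tracks overdue forms but gives no due time for an SAE form.

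**2. Who makes the first judgement.** Adverse Event Reporting does not say. The site is the natural reading, because the clock runs from the site's knowledge and the monitor's review is described as additional. The recipient of the 1-2 day report is not named either.

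**3. What that person knows.** The Protocol description blinds the treating physician and gives assignments only to the independent medical monitor and the site research pharmacists. The documents do not confirm that this monitor is the medical safety monitor of Adverse Event Reporting or the safety monitor of the Data and Monitoring Plan.

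**4. Events attributed to TSC.** The SAE definition includes, for example, inpatient hospitalization whatever the cause. The interval-history rule excludes disease progression. A TSC-attributed admission falls under both, and nothing says which prevails. If the exclusion is applied, the event is in neither column of the table.

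**5. What "related" refers to.** Adverse Event Reporting frames adverse events around study procedures, then refers to participation and to the study when it turns to SAEs. The Data and Monitoring Plan refers to the trial drug. The trigger for the clock is therefore not defined consistently.

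**6. Backstops with a stated frequency.** Visits up to 24 months of age are 6-12 weeks apart. DSMB reports are quarterly (12/4 = 3 months apart). Site monitoring is twice a year (12/2 = 6 months apart). With 24-25 children per randomized group, one event is 1/25 = 4.0% to 1/24 = 4.2% of a group. These figures give the scale; the documents do not show that any SAE form would be delayed for such intervals.

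**The case against.** The strongest reply is that the protocol is not the only operating document. The Manual of Procedures is cited for regular adverse event reporting and may set an entry deadline for all SAEs. This stands as a limit on the finding, which can say only that the protocol states no such deadline. The paragraph that does set SAE timing does not refer to the Manual.

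Second, unrelated SAEs are not left unwatched. Every entered SAE raises an alert beyond the safety monitor, overdue forms are tracked, and a Data Quality Committee reviews monthly summaries. Visual changes have their own route to the site PI and DSMB review. These are real safeguards, but none sets a time for entering an SAE form.

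Third, the threshold is low. A blinded site cannot exclude that a randomized child is on vigabatrin, so many events should qualify as possibly related. That reduces the number affected but does not supply a rule for the rest.

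A reader might also infer that notification of the IRB and lead PIs is filtered by site opinion. The text does not establish this: that sentence follows the one on the monitor's review, so these steps may depend on the monitor's judgement.

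A reader might further infer that reporting delay weakens the safety objective (secondary objective 3). That does not follow. An SAE entered late still reaches the final tabulation, and the safety paragraph promises wider counts and comparisons. Its wording is mixed rather than clearly confined to related events, so it needs clarifying, but that is separate from reporting speed.

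**Conclusion.** The concern holds in this form: the protocol states a reporting deadline only for SAEs considered at least possibly related, its alert for all SAEs depends on a form with no stated entry deadline, and its disease-progression exclusion could keep a TSC-attributed SAE from producing a form. This is more than missing detail, because the written rule itself makes prompt reporting depend on a preliminary opinion.

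The conclusion assumes that the site makes the first relatedness judgement, which is inferred, and that the Manual of Procedures does not already impose a deadline on all SAEs, which cannot be checked. The size cannot be estimated. A reader might want to attach a proportion of drug-related SAEs that would escape the clock, or to conclude that a DSMB review would be distorted, but the documents give no basis for either. The change is a cheap improvement to safety reporting and does not bear on the validity of the efficacy analysis.

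**What to change.** 1. In Adverse Event Reporting, require every event that meets the SAE definition, whatever its attributed cause, to be entered in the DCC system within the existing 1-2 business days of the site's knowledge. Record the site's relatedness opinion as a separate field, and have the safety monitor then judge relatedness.
2. In the opening paragraph of that section, state that the disease-progression exclusion does not apply to events meeting the SAE definition.
3. Reconcile the section with the Data and Monitoring Plan: who makes the first judgement, who receives the report, what relatedness refers to, and whether the differently named monitors are one role. If the Manual of Procedures already sets an all-SAE deadline, cite it and align the wording.
4. In the safety paragraph under Analyses, state that all SAEs are tabulated by arm, with related SAEs as a subset.

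The cost is a protocol amendment, which Human Subject Protection requires the IRB to approve, and faster entry of a few forms. The tracking and alert system is already planned.
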